6.4. Electrocardiogram

Electrocardiogram data will be summarized by ECG parameter. Descriptive statistics will be calculated at baseline and for observed values and changes from baseline at each scheduled time point. Frequency tabulations of the abnormalities will be made.

The ECG variables that will be analyzed are heart rate, PR interval, QRS interval, QT interval, and QT corrected according to Fridericia's formula (QTcF), i.e., $QTcF = QT / \sqrt[3]{RR}$. The Bazett formula will be used for children and adolescent subjects, i.e., $QTcB = QT / \sqrt{RR}$. Descriptive statistics of QTc intervals and changes from baseline will be summarized at each scheduled time point. The percentage of subjects with QTc interval >450 milliseconds, >480 milliseconds, or >500 milliseconds will be summarized, as will the percentage of subjects with QTc interval increases from baseline >30 milliseconds or >60 milliseconds.

Values outside the normal range will be flagged as follows.

- Observed:
 - Heart rate: L <50 bpm; H > 100 bpm
 - RR interval: L < 600 ms; H > 1200 ms
 - QT interval: H > 500 ms
 - QTc interval: H $>$ (450 ms for males, 470 ms for females); increase to >500 ms
- Change from baseline:
 - QTc: 30-60 ms increase; increase >60 ms

All treatment-emergent abnormal findings will be tabulated, displaying the number of subjects with abnormal findings after dosing. An abnormal finding is considered to be treatment-emergent if it occurred during treatment and up to 30 days after the last dose.

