8.3.3. Electrocardiograms

The 12-lead electrocardiograms (ECGs) will be performed at any time during the screening period, as well as Cycle 2 Day 1 and Cycle 4 Day 1. If possible, postdose ECGs should be recorded 2 to 4 hours after the erdafitinib dose on Cycle 2 Day 1 and on Cycle 4 Day 1. Additional ECGs may be performed during the study as clinically indicated.

The subject should rest in a supine position for at least 5 minutes before ECG recording and should refrain from talking or moving arms or legs. A printout of the ECG should be produced and stored in the subject's source documents. The 12-lead ECG recorder device used should have been recently serviced and calibrated. The following variables should be measured: heart rate, RR, QT, PR, QRS, QTc (Fridericia) intervals. QTcF (Fridericia) will be used for assessment of QTc interval. For children and adolescent subjects (aged <18 years), QTc (Bazett) may be used for assessment of QTc interval. The investigator will comment on the clinical relevance and document this in the eCRF (along with details of clinically significant findings).

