The ECG variables that will be analyzed are heart rate, PR interval, QRS interval, QT interval, and QT corrected according to Fridericia's formula (QTcF). The Bazett formula may be used for children and adolescent subjects. Descriptive statistics of QTc intervals and changes from baseline will be summarized at each scheduled time point. The percentage of subjects with QTc interval >450 milliseconds, >480 milliseconds, or >500 milliseconds will be summarized, as will the percentage of subjects with QTc interval increases from baseline >30 milliseconds or >60 milliseconds. All clinically relevant abnormalities in ECG waveform that are changes from the baseline readings will be reported (eg, changes in T-wave morphology or the occurrence of U-waves).

ECOG

ECOG grade will be summarized at each scheduled time point. Descriptive statistics will be calculated at baseline and for observed values and changes from baseline at each scheduled time point.

Bone-related Assessments

Descriptive statistics will be calculated at baseline and for observed values and changes from baseline at each scheduled time point.

[figure not shown]

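### SAP 6.4 corrects QT by Bazett in subjects under 18 and by Fridericia otherwise, but applies one set of QTc limits to both, so two scales can enter the same percentages

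*SAP*

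**What the plan says.** SAP 6.4 lists heart rate, PR, QRS, QT and the Fridericia-corrected QT as the ECG variables to be analyzed, and then states that "The Bazett formula will be used for children and adolescent subjects". Both formulas are written out: Fridericia divides QT by the cube root of RR, Bazett by the square root.

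The limits follow without reference to formula or age: "The percentage of subjects with QTc interval >450 milliseconds, >480 milliseconds, or >500 milliseconds will be summarized", together with "the percentage of subjects with QTc interval increases from baseline >30 milliseconds or >60 milliseconds". A flag list in the same section sets a high QTc at more than 450 ms for males and 470 ms for females.

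The protocol is more permissive. Its ECG procedures (8.3.3) say "For children and adolescent subjects (aged <18 years), QTc (Bazett) may be used for assessment of QTc interval", and its analysis section (9.4.7) says "The Bazett formula may be used for children and adolescent subjects". The protocol's list of measurements carries no age limit: "The following variables should be measured: heart rate, RR, QT, PR, QRS, QTc (Fridericia) intervals".

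Three other places bear on the point:
- **Population.** SAP 6 bases safety analyses on the safety analysis set unless specified otherwise. SAP 2.2.2 puts the Broad Panel, Cholangiocarcinoma Expansion, Exploratory and Pediatric Cohorts into that set. SAP 6.4 names no exception.
- **Broad Panel Cohort.** SAP 1.2 admits subjects from 12 years of age.
- **Entry.** Protocol 5.2, criterion 11, excludes a Fridericia QTc above 480 ms or, for children and adolescents, a Bazett QTc above 440 ms.

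**The concern.** The two corrections give different numbers from the same ECG whenever heart rate is not 60 bpm. A threshold of 450 ms on one scale is therefore not the same criterion as 450 ms on the other. The protocol's entry criterion gives each formula its own limit; the SAP's analysis limits do not.

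If both scales are counted under one QTc heading, the percentage above a limit has no single meaning. A subject under 18 with a fast heart rate could be counted as prolonged when an adult with the same QT and RR would not be. The change-from-baseline rows have a related weakness: under Bazett, a shift in heart rate between visits moves QTc even when the Fridericia value is constant. In a group of about 26 subjects, one crossing is 100/26 = 3.8 percentage points, so a few rate-driven crossings could be read as a QT effect in children.

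**Working it through.** **Inputs.** The formulas, limits and heart-rate flags are from SAP 6.4, the entry limits from protocol 5.2, and the Pediatric Cohort size (20 plus about 6) from SAP 1.2. The heart rates are an assumed range, because the documents give none for subjects under 18.

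**The plan's own figures.** SAP 6.4 flags heart rate below 50 and above 100 bpm, and RR below 600 and above 1200 ms. These agree: 60000/100 = 600 ms and 60000/50 = 1200 ms. No QTc distribution or outlier rate is stated, so there is no such figure to reproduce.

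**Ratio of the two scales.** With RR in seconds, QTcB = QT/RR^(1/2) and QTcF = QT/RR^(1/3), so QTcB/QTcF = RR^(-1/6), with RR = 60/HR. At 80 bpm, RR = 0.75 and the ratio is 0.75^(-1/6) = 1.049. Dividing each limit by the ratio gives the QTcF at which a Bazett value reaches it; for example, 450/1.0491 = 428.9 ms.

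| HR (bpm) | QTcB/QTcF | QTcF when QTcB = 450 | QTcF when QTcB = 480 | QTcF when QTcB = 500 |
|---|---|---|---|---|
| 50 | 0.970 | 464 | 495 | 515 |
| 60 | 1.000 | 450 | 480 | 500 |
| 70 | 1.026 | 439 | 468 | 487 |
| 80 | 1.049 | 429 | 458 | 477 |
| 90 | 1.070 | 421 | 449 | 467 |
| 100 | 1.089 | 413 | 441 | 459 |
| 120 | 1.122 | 401 | 428 | 445 |

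The table needs no assumption about how QTc is distributed. Bazett is the higher scale above 60 bpm, equal at 60, and the lower one below.

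**Change from baseline.** Hold QTcF at 400 ms, so that only heart rate changes:
- 70 to 110 bpm: Bazett goes from 410.4 to 442.5 ms, an increase of 32.1 ms, which passes the 30 ms row.
- 80 to 100 bpm: 419.6 to 435.5 ms, an increase of 15.9 ms.
- 100 to 80 bpm: a decrease of 15.9 ms.

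The Fridericia change is zero in all three.

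**From the entry limit.** A subject at the highest Bazett value allowed at entry, 440 ms, reaches 450 ms at constant QTcF if heart rate rises by the factor (450/440)^6 = 1.144, for example from 80 to about 92 bpm (80 × 1.144 = 91.5).

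**With one formula.** If QTcF is used for everyone, the ratio is 1.000 at every heart rate and each limit means the same in every row.

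**The case against.** The strongest reply is that the SAP never says the two scales share a table. SAP 6.4 summarizes by ECG parameter and gives QTcF and QTcB separate names and formulas. SAP 2.2.5 provides for a separate safety evaluation of the Pediatric Cohort, which includes the Broad Panel adolescents. SAP 2.3 defines age subgroups that may be used for safety. Table shells could keep the scales apart.

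That stands as far as it goes: mixing follows from the default populations and is not stated. But the separate pediatric evaluation does not remove subjects under 18 from the pooled safety set, or adolescents from the Broad Panel Cohort. No instruction in SAP 6.4 keeps the formulas apart when its limits are applied.

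A reader might also infer that Bazett replaces Fridericia as the only pediatric value. The text does not say so. QTcF is listed for analysis without an age limit, and Bazett is then added. This is an ambiguity, made worse by the difference between *will* in the SAP and *may* in the protocol.

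Third, heart rate and uncorrected QT are summarized too, and the flags include "Heart rate: L <50 bpm; H > 100 bpm", so a rise to 110 bpm would be visible. This helps in that example. It does not help at 80, 90 or 100 bpm, none of which is above the flag.

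Finally, Bazett in children is consistent with the entry criterion, scheduled on-treatment ECGs are few (Cycle 2 Day 1 and Cycle 4 Day 1), and nothing inferential depends on them. All true; these points limit the importance of the matter but do not resolve it.

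**Conclusion.** The point holds as a low-cost improvement to descriptive safety tables. The plan names two correction formulas by age, gives one set of limits, and does not say that the results are to be kept apart. The size of the discrepancy on a given ECG is exact: 4.9%, 7.0% and 8.9% at 80, 90 and 100 bpm. That it would run upward in this trial assumes pediatric heart rates above 60 bpm, which the documents do not report.

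Three stronger conclusions are not supported:
- **That pediatric percentages are raised by heart rate as such.** The direction depends on whether the rate is above or below 60 bpm. The change rows rise only if heart rate rises on treatment, and fall if it drops.
- **That a particular number of subjects would be misclassified.** Any count needs a QTc distribution that the documents do not give, and subjects under 18 enter only with a Bazett value of at most 440 ms.
- **That pediatric percentages would exceed adult ones.** Adults may enter with a Fridericia value up to 480 ms. The comparison that the arithmetic supports is Bazett against Fridericia in the same subject.

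About 26 subjects are concerned, and no primary or secondary efficacy result is affected.

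**What to change.** In SAP 6.4:
- Tabulate QTcF for all subjects, including those under 18, in the threshold, flag and change-from-baseline summaries.
- Show QTcB for subjects under 18 in a separate table labelled with the formula.
- State that the two are not pooled under a single QTc heading.
- Reconcile the SAP's *will* with the *may* in protocol 9.4.7 and 8.3.3, so that both documents describe the same pediatric analysis.

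This concerns tabulation only. Entry limits and site ECG practice stay as they are. The cost is one derived variable, computed from QT and RR that are already collected, and one additional pediatric table.

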6.5. Vital Signs and Physical Examination Findings

All clinically significant abnormalities will be recorded as AEs and summarized for safety.

6.6. Other Safety Measures

Frequencies of performance score will be reported over time. Descriptive statistics of change in performance scores from baseline will also be provided.

Descriptive statistics for bone-related assessments will be provided at baseline, at each scheduled visit and changes from baseline at each scheduled time point.

Pregnancy testing results will be presented in a by-subject listing.

7. PHARMACOKINETICS (PK)

Details of population PK analysis, analysis to evaluate relationships between plasma concentration or metrics of systemic exposure and CYP2C9 polymorphism, markers of pharmacological activities (serum phosphate), efficacy or treatment-emergent adverse events may be explored as data allow using population approaches. If relevant, these analyses will be presented in a separate plan and results will be presented in a separate report. All subjects and samples excluded from the analysis will be clearly documented in the separate study report.

Plasma and CSF pharmacokinetic data will be listed for all subjects with available plasma erdafitinib concentrations. Concentration values below the lower limit of quantitation (LLOQ) will be displayed in listings as zero with a flag and handled as zero. Plasma protein binding data such as alpha-1-acid glycoprotein and fraction unbound (unitless) of erdafitinib based on assessment on C2D1 2-4 hour postdose will be listed for all subjects.

For Pediatric Cohort, an interim Bayesian population PK analysis and, if appropriate, NCA analysis of plasma concentration-time data for erdafitinib and markers of pharmacological activities (e.g., serum phosphate) will be performed after 5 children or adolescents (<18 years of age) are enrolled and have completed Cycle 3 Day 1 visit in the study (see protocol Section 9.4.4). In addition, further interim analyses may be conducted after enrollment of additional subjects. Descriptive statistics, including arithmetic and geometric mean, median, standard deviation, coefficient of variation (CV), geometric CV, minimum and maximum, will be tabulated for erdafitinib PK concentrations and protein binding data by time point and age groups (children [6 to <12], adolescents [12 to <15 years of age, 15 to <18 years of age]). PK and protein binding summary table will be performed based on PK analysis set.

8. BIOMARKERS

The following analyses may be provided with a focus on the treated population in the Broad Panel Cohort.

- Summary and listing of baseline FGFR alterations (alteration types, genes, and variants) will be provided.

- Sensitivity efficacy analysis (see 5.2.3.3 for more details) will be performed excluding patients without an eligible FGFR alteration, with only known or suspected FGFR germline mutations, with only FGFR fusion with a 5-prime partner, with gatekeeper/resistance FGFR alterations, or with exclusionary co-alterations, as specified in the protocol (a corresponding listing of the excluded patients will be provided).
- A co-alteration profile will be provided by tumor histologies, and by FGFR alterations (alteration types, genes, and variants). Additional analyses such as response association may be conducted.
- Biomarker positive frequency based on central screening (with patients who were enrolled by central screening) results will be summarized by tumor histology.

Additional exploratory biomarker analyses may be performed based on the Exploratory Cohort.

APPENDIX

The appendix includes details about the BHM, simulation assumptions and design setups, operating characteristics for Broad Panel Cohort only and with multiplicity adjustment for Core Panel Cohort.

A.1. Bayesian Hierarchical Model (BHM)

Denote $\pi_g = \Pr(\text{response}|\text{treatment}, g)$, the BHM models the log-odds of response (i.e. ORR) defined as

$$\theta_g = \text{logit}(\pi_g) = \ln\left(\frac{\pi_g}{1 - \pi_g}\right)$$

with weak priors

$$\begin{aligned}\theta_g &\sim N(\mu, \tau^2) \\ \mu &\sim N(-2.19, 2^2)\end{aligned}$$

$\tau^2 \sim \text{Inverse Gamma distribution with mean 2 and weight 0.75.}$

The prior normal mean value of -2.19 for μ corresponds to the logit of 10%. The prior distribution of μ is shown in [Figure A1a](#), and it corresponds to a log odds range of 0% to 99.7%. The parameter τ represents the degree of heterogeneity between the tumor histology groups, thus the degree of borrowing. At one extreme, when τ is 0, there is complete borrowing. At the other extreme, when τ is near infinity, there is no borrowing across the groups. For values between these two extremes, there is an amount of borrowing consistent with the variability across groups. The mean for τ is set to the same value as the prior standard deviation for μ , and the weight is set to be 0.75. The distribution of τ is shown in [Figure A1b](#). It is to ensure certain degree of borrowing.

[figure not shown]

Figure A1: Prior Distribution of Hyperparameters of BHM. a) Prior Distribution of μ . b) Prior Distribution of τ

A.2. Simulation Assumptions and Setups

The simulation study in this section is based on the Broad Panel Cohort which enrolls patients with target FGFR mutations or any gene fusion, considering three protocol specific interim futility analyses and the primary analysis. Note that there will be an efficacy assessment at the second

interim, but it is not considered in the simulation for its ignorable impact with a use of an alpha of < 0.01% in the proposed early success rule. The simulation study has the following assumptions and parameter setups.

Assumptions on Prevalence

The alterations eligible for inclusion in the Broad Panel Cohort consist of target FGFR mutations and any FGFR fusion. The full list of target FGFR mutations eligible for the Broad Panel Cohort will be provided separately on the study portal and in the laboratory manual. Based on the predicted frequency of target FGFR alterations, prevalence of tumor histology, and predictive modeling of distribution; the tumor histologies that were selected for central molecular screening include: glioblastoma; squamous non-small cell lung cancer; squamous cell head and neck cancers; gastric cancer; breast cancer; cholangiocarcinoma; soft tissue sarcoma; cervical, and ovarian cancers; glioma; renal cell cancer; esophageal cancers; hepatocellular carcinoma; and pancreatic cancer (Table A1).

Table A1: Frequency of Preclinically Validated Target FGFR Mutations and Fusions in Advanced Cancer

Advanced Cancer Type	Target FGFR Frequency ^a	TOTAL G7, Drug Treated Patients L2+ ^b	Anticipated tumor representation in CAN2002 in L2+ FGFR+ population plus 'Other' Group
Glioblastoma	~21%	16317	~18%
Squamous non-small cell lung cancer	~4%	85177	~18%
Squamous cell head and neck cancers	~9%	25315	~13%
Gastric cancer	~3%	78760	~13%
Breast cancer	~2%	86180	~10%
Cholangiocarcinoma	~11%	8245	~5%
Endometrial	~7%	10482	~4%
Glioma	~5%	13836	~4%
Ovarian cancer	~2%	31363	~3%
Soft tissue sarcoma	~8%	5485	~2%
Renal cell cancer	~1%	43431	~2%
Cervical cancer	~3%	5263	~1%
Esophageal cancer	~1%	22467	~1%
Hepatocellular carcinoma	~2%	10042	~1%
Pancreatic	<1% ^c	-	-
Other	-	-	~5% ^d

Note: a. FGFR mutations and fusions are from The Cancer Genome Atlas (TCGA) and Genomics Evidence Neoplasia Information Exchange (GENIE) databases accessed February 2019, and filtered for FGFR hotspot mutations and likely pathogenic FGFR fusions. Target refers to FGFR mutations and fusions predicted to be likely pathogenic based on genomic features.

b. G7=US, France, Germany, UK, Spain, Italy and Japan, and the treated patients of second and higher line include those are incident or newly recurrent across all these countries.

c. Based on clinical experience.

d. Assumed for simulation purpose

In the simulation studies, all selected central molecular screening tumor histologies are assumed for enrollment except pancreatic cancer due to its neglectable FGFR frequency (~0%) based on The Cancer Genome Atlas (TCGA) and Genomics Evidence Neoplasia Information Exchange (GENIE) databases. In addition, the trial allows enrollment of local molecular screening FGFR+ subjects and the tumor histologies that are not limited to the ones listed in [Table A1](#). Thus a group named ‘Other’ is included in the analysis to take in all other tumor histologies not listed in [Table A1](#). Considering the uncertainty of the composition in the group Other, it will not stop early for enrollment for interim futility while the same cap of 30 applies. Final futility assessment will be done on the group Other before being pooled for primary efficacy analysis.

The proportion of each tumor histology for enrollment into the trial is listed in the last column in [Table A1](#). In particular, a 5% proportion is assumed for the group Other. Note that other operational factors such as trial countries, open sites, investigators, etc. are not considered into the prevalence assumption.

Assumptions on Accrual Rate

A peak accrual rate of 5 subjects/week with ramp up is assumed. Ramp up defines periods of simple linear increase in the mean recruitment rate from the start of trial accrual. The mean weekly accrual rate is shown in [Figure A2](#). During simulation, a Poisson process was used to simulate the random arrival of subjects with the specified mean accrual rate.

[figure not shown]

Figure A2: Mean Weekly Accrual Rate Over Time

Parameter Setups

- Sample size: 200 (Response-evaluable Population)
- Cap (Maximum sample size) on each tumor histology: 30
- Three Interim analyses at 60, 100, 140 response-evaluable subjects having completed a specified visit (with 6 weeks to final endpoint)

- Minimum number of subjects required before interim futility stop in a given histology group: 5
- Futility criteria: Less than a 40% chance that $\text{ORR} > 25\%$ (i.e. posterior $\text{Pr}(\text{ORR} > 25\%) < 40\%$)
- Success criteria at the primary analysis: Greater than an 80% chance that $\text{ORR} > 25\%$ (i.e. posterior $\text{Pr}(\text{ORR} > 25\%) > 80\%$)
- Follow-up of enrolled subjects is allowed after tumor histology group stopped enrollment due to futility
- No assumption on dropout

Note that the futility threshold 40% and the success threshold 80% were justified through extensive simulations to achieve good balance of design operating characteristics under various scenarios.

A.3. Operating Characteristics

The following simulations results are based on the Broad Panel Cohort only with no multiplicity adjustment. All scenarios were conducted using the FACTS v6.2 Enrichment Design – Dichotomous engine and the results from FACTS are post-processed in R.

A.3.1. Scenarios

As mentioned in section A.2., 14 tumor histologies and one Other group were assumed for enrollment. Below we use the shorthands: GBM (glioblastoma), Lung (squamous non-small cell lung cancer), HN (squamous cell head and neck cancers), Gastric (gastric cancer), Breast (breast cancer), Cholangio (Cholangiocarcinoma), Endometrial (endometrial cancer), Glioma (glioma), Ovarian (ovarian cancer), and STS (soft tissue sarcoma), RCC (renal cell cancer), Cervical (cervical cancer), Esophageal (Esophageal cancer), and Hepatocellular (hepatocellular cancer). Table A2 lists the simulation scenarios. The percentage number under each tumor histology is the proportion of the tumor histology in the trial assumed for enrollment (see Table A1 for details). The scenarios are based on the assumed true ORR for each tumor histology. Six scenarios are shown, with different true ORRs for each histology and the group Other. The last column of Table A2 shows the (prevalence) weighted average ORR as the overall truth assumed on the original tumor agnostic pool (the Broad Panel Cohort before possible futility on any tumor histologies).

More specifically, the simulation scenarios include:

- **Global Null:** the true ORRs for all tumor histologies and the group Other are 15% at the boundary of the null hypothesis (i.e., $\text{ORR} \leq 15\%$). Under this scenario, all tumor histologies and the original tumor agnostic pool are nonactive and should not succeed as a pool after futility analysis at the primary efficacy analysis.
- **Alternative:** the true ORRs for all tumor histologies and the group Other are 35%, at the boundary of the alternative hypothesis (i.e., $\text{ORR} \geq 35\%$). Under this scenario, all tumor

histologies and the original tumor agnostic pool are active and expected to succeed as a pool after futility analysis at the primary analysis.

- **Target:** the true ORRs for all tumor histologies and the group Other are 25%, the target ORR for BHM posterior probability. Under this scenario, all tumor histologies and the original tumor agnostic pool are active and expected to succeed as a pool after futility analysis at the primary analysis.
- **Half-Half Other35:** the most prevalent half of the tumor histologies are nonactive with ORR at 10%, the rest half are active with ORR at 35%, and the group Other is active with ORR at 35%. Under this scenario, the original tumor agnostic pool is nonactive with a weighted ORR of approximately 15%. However, the pool for the primary efficacy analysis with tumor histologies that didn't meet the futility criteria is possible to be active.
- **Half-Half Other15:** the most prevalent half of the tumor histologies are nonactive with ORR at 10%, the rest half are active with ORR at 35%, and the group Other is nonactive with ORR at 15%. Under this scenario, the original tumor agnostic pool is nonactive with a weighted ORR of 14%. However, the pool for the primary efficacy analysis with tumor histologies that didn't meet the futility criteria is possible to be active.
- **Cholangio35:** Cholangiocarcinoma is the only active tumor histology with ORR at 35%, GBM and Lung have ORR of 10%, and all others are with 15% ORR. Under this scenario, the pool is nonactive with weighted ORR 14%. However, the pool for the primary efficacy analysis with tumor histologies that didn't meet the futility criteria is possible to be active.

The Global Null scenario is to evaluate the false positive rate (FPR) for the primary pooled efficacy analysis and the family-wise error rate (FWER) with BHM analysis. The scenarios Alternative and Target are for power assessment. The scenarios Half-Half Other35, Half-Half Other15, and Cholangio35, with their original tumor agnostic pooled ORR at the null, are designed to assess the impact of futility and to evaluate the FPR for the primary pooled efficacy analysis. Note that scenarios with original pooled ORR $> 15\%$ can also be designed but are of less interest to be investigated for power assessment thus are not discussed here.

Table A2: Simulation Scenarios Based on ORR for Individual Tumor Histologies

Scenario	GBM	Lung	HN	Gastric	Breast	Cholangio	Endometrial	Glioma	Ovarian	STS	RCC	Cervical	Esophageal	Hepatocellular	Other	Pooled
Global Null	0.15	0.15	0.15	0.15	0.15	0.15	0.15	0.15	0.15	0.15	0.15	0.15	0.15	0.15	0.15	0.15
Alternative	0.35	0.35	0.35	0.35	0.35	0.35	0.35	0.35	0.35	0.35	0.35	0.35	0.35	0.35	0.35	0.35
Target	0.25	0.25	0.25	0.25	0.25	0.25	0.25	0.25	0.25	0.25	0.25	0.25	0.25	0.25	0.25	0.25
Half-Half	0.10	0.10	0.10	0.10	0.10	0.10	0.10	0.35	0.35	0.35	0.35	0.35	0.35	0.35	0.35	0.15
Other35																
Half-Half	0.10	0.10	0.10	0.10	0.10	0.10	0.10	0.35	0.35	0.35	0.35	0.35	0.35	0.35	0.35	0.14
Other15																
Cholangio35	0.10	0.10	0.15	0.15	0.35	0.15	0.15	0.15	0.15	0.15	0.15	0.15	0.15	0.15	0.15	0.14

Note: Bold indicates the active (ORR>15%) tumor histologies; no bold represents the nonactive (ORR≤15%).

A.3.2. Definitions of Operating Characteristics

The following terminology will be used to discuss operating characteristics of the BHM analysis.

Selection Power

Selection power is the proportion of simulations that selected at least a given percentage of active tumor histologies (e.g. 80%) to be pooled for the primary efficacy analysis.

Proportion of Success

Proportion of success is the proportion of simulations in which BHM claimed at least one tumor histology as a success. Similarly, the success criteria ($\text{Pr}(\text{ORR} > 25\%) > 80\%$) is used for BHM to claim a success (efficacy) for a given tumor histology.

Family-wise Error Rate (FWER)

FWER represents the proportion of simulations in which BHM claimed false-positive efficacy in one or more of the nonactive tumor histologies. Note that the success criteria ($\text{Pr}(\text{ORR} > 25\%) > 80\%$) is used for BHM to claim a success (efficacy) for a given tumor histology.

The following terminology is used to discuss the exact binomial test in the pooled primary efficacy analysis.

Power

Power is calculated as the proportion of simulations claiming a success (efficacy) on the pooled data of primary efficacy analysis.

False Positive Rate (FPR)

FPR is defined as the proportion of simulations claiming a false-positive success (efficacy) on the pooled data of the primary efficacy analysis. Note that a success is false-positive only when the weighted average of true ORRs is less than 15% for the remaining histologies that didn't meet the futility criteria in the pool for primary efficacy analysis. The weights are the renormalized assumed prevalence in [Table A1](#) for each tumor histology that ended up in the pool.

Mixing Nonactive

Mixing nonactive is defined as the proportion of claiming a success (efficacy) in the pooled data at the primary efficacy analysis that is mixed with at least one nonactive histology.

A.3.3. Operating Characteristics Results

20000 simulation runs were conducted to evaluate the operating characteristics of the proposed design.

Selection Power under The Alternative Scenario (Sample Size Determination)

The selection power under the Alternative scenario was used for sample size determination. As mentioned in section 1.4., the sample size of 200 response-evaluable subjects for the Broad Panel Cohort is justified based on extensive simulations with various Bayesian hierarchical model (BHM) designs to achieve approximately 80% power to select at least 80% tumor histologies (e.g., ≥ 12 of 15 tumor histologies) in the Alternative scenario (true ORR at 35% for all histologies). The selection power for Alternative scenario under the proposed design is shown in [Figure A3](#). The probability of selecting more than 12 active histologies for the pooled primary analysis is approximately 83%; the probability of selecting at least 10 active histologies is approximately 95%; the probability of selecting all 15 active histologies groups dropped to 29.4%.

[figure not shown]

Figure A3: Selection Power for Alternative Scenario

Power and Proportion of Success

The power based on pooled efficacy analysis and the proportion of success based on BHM are listed in [Table A3](#) for all scenarios. Note that the proportion of success and the power in the first row of Global Null represent the FWER and FPR and will be discussed the next. The design is achieving above 99% power and proportion of success for scenario Alternative; For scenario Target, it achieves above 95% while has a moderate proportion of success of 70%; The scenario Half-Half Other35 achieves 99% power and 94% proportion of success; The power and proportion of success for the scenario Half-Half Other15 are approximately 98% and 87%; The power and proportion of success for scenario Cholangio35 are lower than 50%, note that if the ORR for Cholangio is 50% with other ORRs remaining the same, the power and proportion of success will increase to approximately 83% and 77% respectively (not listed as one scenario).

Duration of the Trial

The expected trial duration listed in [Table A3](#) varies among different scenarios mainly based on whether the relatively high prevalent tumor histologies are active or not. In the Alternative scenario when all tumor histologies are active, it is unlikely that the high prevalent tumor histologies will stop enrolment early, thus these histologies reach the cap easily and the maximum sample size of 200 is fulfilled in a shorter duration. Similar to the Alternative scenario, the Target scenario has a relatively short duration with all active tumor histologies. In comparison, for the other three scenarios, tumor histologies with high prevalence are assumed nonactive thus likely to be stopped early. Since the remaining low prevalent tumor histologies will enroll subjects at a much slower rate, longer trial durations will result. Note that the duration numbers (in weeks) are for comparison among scenarios to study the impact of early futility on accrual, and are not intended to be a definitive reference on actual trial duration.

FWER and FPR

The FPR based on pooled efficacy analysis and FWER based on BHM are listed in [Table A4](#) for all scenarios.

- **FWER**

The FWERs for all scenarios are well controlled at 5% level. Specifically, the FWERs are 3.53% under Global Null, 0.24% under Half-Half Other35, 0.60% under Half-Half Other15, and 4.15% under Cholangio35.

As mentioned in section [5.2.3.2.](#), the posterior probability of ORR > 25% for each individual tumor histology will be evaluated as a supplementary analysis. In the simulation results, the posterior probability of ORR > 25% is not reported. Instead, the probability of declaring efficacy on each individual tumor histology is listed in [Table A4](#) (Columns 2-11) based on success criteria ($\text{Pr}(\text{ORR} > 25\%) > 80\%$) as an evaluation of the BHM as well as the possible supplementary analysis of the study.

- **FPR and Mixing Nonactive**

It is shown that the FPR for pooled analysis is around 18.57% for Global Null scenario. Among the false positive cases, there are 16.34% false positive cases that include group Other that did not have interim futility analyses, and 36.7% false positive cases that include at least 1 group with less than 5 subjects. For the Half-Half Other35 scenario, the FPR is controlled at 0.08%. For the Half-Half Other15 scenario, the FPR is controlled at 0.71%. For the Cholangio35 scenario, FPR is at 7.42%. The reasonable FPR control on scenarios Half-Half Other35, Half-Half Other15, and Cholangio35 are aided by the interim and final futility analysis before pooled efficacy analysis, thus helping to prune original tumor agnostic pool with $\text{ORR} < 15\%$ to the final tumor pool with $\text{ORR} > 15\%$ by excluding those tumor histologies that met the futility criteria from final pooling.

Another aspect to consider is the proportion of mixing nonactive tumor histologies for success on pooled data. For the scenarios Half-Half Other35, Half-Half Other15 and Cholangio35, the proportions of mixing nonactive are 19.8%, 23.5%, and 36.1% respectively. Noticing that these scenarios have a considerable number of nonactive tumor histologies, the pooled efficacy analysis may not be performed at the primary analysis if a large amount (e.g. 50%) of tumor histologies were stopped for enrollment.

Note that the FPR for scenario Global Null is inflated as 18.57% and the scenario Alternative is overpowered with power 1, different alpha levels for testing are investigated in [Table A5](#). An alpha level of 0.005 will lower the FPR under 10% while maintaining strong power for both Alternative and Target scenarios. An alpha level of 0.001 will lower the FPR under 5% while moderately sacrificing the power for scenario Target.

Summary

Based on the operating characteristics of different scenarios, the proposed design outlined in this study will have a control of FPR for Half-Half Other35 (0.08%) and Half-Half Other15 (0.71%), and a moderate control of FPR for Cholangio35 at 7.42%, while the FPR for the Global Null is 18.57%. In addition, it achieves a satisfactory performance in terms of testing power (e.g., above 95% power and proportion of success for scenario Alternative) and selection power (approximately 85% power to select at least 80% tumor histologies for scenario Alternative).

Table A3: Operating Characteristics for Duration of the Trial, Ppn of Success, and Power

Scenario	Expected Duration of the Trial (weeks)	Ppn of Success	Power
Global Null	251	0.0353	0.1857
Alternative	58	0.9982	1
Target	100	0.7075	0.9763
Half-Half Other35	157	0.9352	0.9966
Half-Half Other15	163	0.8660	0.9816
Cholangio35	219	0.3206	0.4974

Note: Proportion of success is the proportion of simulations in which BHM claimed at least one tumor histology as a success. Power is calculated as the proportion of simulations claiming a success (efficacy) on the pooled data of the primary efficacy analysis.

Table A4: Operating Characteristics for FWER and FPR

Scenario	Probability Erda Will be Declared Successful in Each Histology by BHM										Pooled Analysis							
	GBM	Lung	HN	Gastric	Breast	Cholangio	Endometrial	Ovarian	STS	RCC	Cervical	Esophageal	Hepatocellular	Other	FWER	FPR	Mixing Nonactive	
Global Null	0.002	0.002	0.002	0.002	0.002	0.002	0.002	0.002	0.002	0.004	0.003	0.004	0.003	0.003	0.0353	0.1857	-	
Alternative	0.608	0.611	0.580	0.572	0.547	0.477	0.450	0.451	0.415	0.364	0.359	0.285	0.280	0.281	0.500	-	-	
Target	0.116	0.121	0.108	0.107	0.103	0.101	0.104	0.101	0.097	0.086	0.083	0.060	0.057	0.060	0.121	-	-	
Half-Half Other35	0.000	0.000	0.000	0.000	0.000	0.001	0.001	0.001	0.378	0.351	0.313	0.310	0.219	0.215	0.217	0.507	0.0024	0.0008
Half-Half Other15	0.000	0.000	0.000	0.000	0.000	0.000	0.000	0.000	0.360	0.334	0.295	0.290	0.200	0.202	0.200	0.004	0.0060	0.0071
Cholangio35	0.000	0.000	0.002	0.002	0.299	0.003	0.003	0.003	0.003	0.004	0.005	0.006	0.005	0.005	0.003	0.0415	0.0742	0.3606

Note: the bold numbers represent the power to declare efficacy in a given active tumor histology; no bold numbers represent the false-positive rate to declare efficacy in a nonactive tumor histology.

FWER represents the proportion of simulations in which BHM claimed false-positive efficacy in one or more of the nonactive tumor histologies.

FPR is defined as the proportion of simulations claiming a false-positive success (efficacy) on the pooled data of the primary efficacy analysis.

Table A5: FPR and Power across Different Alpha Level

Alpha	FPR under Scenario Global Null	Power under Scenario Alternative	Power under Scenario Target
0.025	0.1857	1	0.9763
0.02	0.1635	1	0.9721
0.015	0.1444	1	0.9678
0.01	0.1225	1	0.9604
0.005	0.0850	1	0.9456
0.001	0.0373	1	0.8878

A.4. SEPARATE EFFICACY ANALYSIS FOR JAPAN SUBMISSION

